#### B. Feasibility:

The following feasibility data will be collected and assessed :

- 1) Recruitment:
  - a. Recruitment sites (number, location, and method of their selection)
  - b. Factors influencing recruitment rate
  - c. Methods used for subject recruitment
  - d. Number of subjects:
    - I.
      - i. Initially contacted
      - ii. Initial interviewed
      - iii. Consented
      - iv. Baseline data collected
  - e. Reasons for non-participation:
    - i. After initial contact and/or initial interview
    - ii. After consent process
    - iii. After initial data collection or throughout the study
    - iv. Until end of study
  - f. Reasons for participating in and completing study

2) Randomization:

- a. Testing effect of randomization process on distribution of demographic, co-morbidity, and other background characteristics
- f. Testing randomization process on their baseline main outcomes
- g. Examining acceptability of the randomization process and its effect

3) Missing data:

- a. Differences in rates of missing data between medication and placebo groups and per time point
- b. Pattern of missing data

4) Retention rate:

- a. Differences in retention between medication and placebo groups
- b. Factors influencing these differences

5) Subjects' satisfaction with:

- a. Study procedures
- b. Study implementation and staffing
- c. Medication delivery methods
- d. Data collection timepoints and outcomes

6) Medication fidelity with:

- a. Delivery methods
- b. Number of successful and failed deliveries
- c. Assessment methods
- d. Timing and method of feedback

7) Study improvement procedures/maintaining documentation of:

- a. Study/protocol development, revision, and modification
- b. Issues and concerns with implementing recruitment strategies
- c. Issues and concerns with accessing, distributing, and tracking of medication and placebo
- d. Issues and concerns with measurements:
  - i. Number of measurements
  - ii. Time requirements of measurements
  - iii. Redundancy among measurements
  - iv. Positive or negative carryover

Sub-study 1c: FoTv vs placebo for use as an adjunct to COVID-19 vaccination.

The primary objectives of this study are to determine whether FoTv, when taken for four consecutive days starting the day of COVID-19 vaccination, is safe and associated with:

- An enhanced peak COVID-19 antibody response
- A reduced rate of post-peak antibody decline
- Reduction in side effects from COVID-19 vaccination

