## **9. RESEARCH DESIGN AND METHODS**

The following research design applies to each of the following studies:

Sub-study 1a: FoTv vs. placebo for acute COVID-19 patients

Sub-study 1b: QFPD vs. placebo for acute COVID-19 patients

Sub-study 1c: FoTv vs. placebo as an adjunct to COVID-19 vaccination

Sub-studies 1a and 1b of Phase 1 trial will each be 2-arm multicenter double blind randomized placebo controlled clinical trials.

Each of these safety/feasibility sub-studies will be conducted identically with the exception of additional exclusion criteria that will be required for sub-study 1b on account of the presence of herbal components including ephedrine that require these precautions for avoiding herb-drug interactions.

Sub-study 1c will be a single site double blind randomized placebo controlled clinical trial.

This will be a shorter intervention with broader inclusion criteria.

The research design and methods for the larger efficacy trial (Phase 2) will require analysis of these first two feasibility studies, and the final protocol will be submitted as a future amendment.

The primary objective of sub-studies 1a and 1b will be to assess the safety of FoTv or mQFPD, respectively, when used as therapies for acute COVID-19 infection and feasibility of the study protocol.

The primary objectives of sub-study 1c will be to ascertain the safety of FoTv when used as an adjunct to standard COVID vaccination as well as to evaluate its effects on post-vaccine COVID-19 antibody titers and on vaccination-related side effects.

A total of 66 subjects (33 FoTv or mQFPD and 33 placebo) will be enrolled in each of the 1a and 1b sub-studies.

A total of 266 subjects (133 FoTv and 133 placebo) will be enrolled in sub-study 1c.

The study protocol will be implemented and safety, feasibility, clinical, and laboratory data will be collected.

Interested participants will be asked to contact the study team, who will then conduct screening, consenting, and study enrollment. The study will be open to patients who are

- a) Mildly-to-moderately symptomatic and have tested positive for COVID-19 (sub-studies 1a and 1b)
- b) Scheduled for COVID-19 vaccination (sub-study 1c).

See section 11 for recruitment plan.

Once their eligibility has been confirmed, participants will be randomized to one of two groups by the study statistician:

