### Test Product Dose and Route of Administration

Participants in sub-studies 1a and 1b: The dosage of FoTv or mQFPD is 8 capsules three times a day for 14 consecutive days. It does not need to be consumed with food. It is best taken at least 30 minutes before OR at least 60 minutes after meals, in the morning, noon and evening. Accidentally missed doses will not need to be taken at a later time, but will be recorded in a daily diary. Should swallowing capsules be an issue, they can be opened and dispensed into water or juice for easy ingestion.

Participants in sub-study 1c: The dosage of FoTv is 8 capsules three times a day for 4 consecutive days ((starting with the day of the first vaccination). It does not need to be consumed with food. It is best taken at least 30 minutes before OR at least 60 minutes after meals, in the morning, noon and evening. Accidentally missed doses will not need to be taken at a later time, but

will be recorded in a daily diary. Should swallowing capsules be an issue, they can be opened and dispensed into water or juice for easy ingestion

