### **Statistical Methods And Considerations**

For all sub-studies (1a, 1b, and 1c), data management and statistical analysis will be performed by the Krupp Biostatistical and Data Management Core and will employ the Krupp Data System (KDS). A computer-generated randomization list will be prepared by the study biostatistician and will be used to randomize subjects into one of the two treatment groups with equal probability. For sub-study 1c only, equal number of subjects based on age (18-55 and  $>55$ ) and BMI ( $<30$  and  $\geq 30$ ) will be randomized to the treatment groups. For all sub-studies, randomization tables will be prepared at the beginning of the study and will be maintained by the study biostatistician.

Within each of the sub-studies, the comparability of the two treatment groups in terms of baseline demographic and clinical features will be tested with analyses of variance (ANOVAs) for continuous variables and Chi-square analyses for dichotomous variables. Descriptive statistics and exploratory graphing will be used to assess the distribution, normality, and homogeneity of the data. If needed and applicable, the continuous outcome data will be transformed using an appropriate transformation such as a log transformation. Missing data will be examined to assess randomness and informativeness using methods developed by Diggle (1989). Similarly, we will test whether dropout is random or systematic by comparing the dropouts with the study completers in terms of the baseline data. An absence of significant differences would support the random nature of dropout.

The primary aims of our data analytic strategy will be directed toward assessing the safety of the interventions, antibody titers, vaccine side effects, adherence to treatment, and retention rate. This will help to provide guidance to inform any

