required methodological modifications. The safety data will be summarized by treatment group and site. Adverse events will be tabulated. These will include the number of participants for whom the event occurred, the rate of occurrence, and the severity and relationship of adverse events to study treatment. Safety data will be analyzed using ANOVAs for continuous variables and Chi-square analyses for dichotomous variables at each time point. Wilcoxon-Mann-Whitney rank-sum test will be used to analyze treatment arm versus control arm across study visits and sites. We anticipate using non-parametric tests because the majority of the outcome measures used in our research may not be normally distributed. The Kruskal-Wallis test will be used to determine whether samples from each of the two arms originated from the same distribution. Since nonparametric tests are based on complete data and ignore missing follow-up data, general linear mixed regression modeling (Gibbons et al, 1988; Hedeker et al, 199; Laird et al, 1982) will be used to confirm the results of the nonparametric tests. The two arms will be compared over time with a focus on the treatment by Time interaction effect. Mixed regression modeling offers robust handling of missing data (Little, 1996) with an assumption that the data is missing at random. This method allows the inclusion of subjects with missing data or those who were terminated early in the study, without relying on data imputation procedures. This method provides an estimate of the individual variability around the population trend, the variability of the individual intercepts (baseline values) and slopes (changes across time), and the correlation between them. Co-variance structure will be chosen based on Akaike's Information Criterion (AIC). Random group level treatment effects will also be evaluated for importance based on the model AIC. Denominator degrees of freedom will be calculated using the Kenward-Roger small sample correction.

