A detailed list of feasibility outcomes is provided in the previous section. Briefly, feasibility outcomes will be assessed by determining: 1) Numbers of potentially eligible and ineligible patients, number contacted, and consent rates. 2) Feasibility of recruiting sites in which staff are interested in participating in a future main trial. 3) Rate of retention in the trial, including response rates to questionnaires and individual measures. 4) Intervention fidelity and adherence using case report forms and patient-completed personal diaries. 5) Determining the primary outcome measure for the main trial by assessing and comparing sensitivity to change of the measures and other statistical properties, comparing follow-up rates of different methods of data capture and of individual measures, and evaluating which outcome measures best reflect the patients' recovery goals, as identified from the collected data.

As indicated above, the primary aims of our data analytic strategy for sub-studies 1a and 1b will be directed toward examining the safety and feasibility of the treatments. Although it is not our major focus, we also aim to estimate effect sizes to assist in future power calculations. However, recent work by Kraemer (2006) has highlighted important limitations of this aim due to the large standard error surrounding the pilot study effect size. As a result, the primary focus of our analyses will remain on safety and feasibility and we will report our findings with this limitation in mind. Our goal is to collect important data regarding our ability to implement recruitment strategies, and the safety and feasibility of the treatments and measurements. Information derived from this research will lead to better-designed full-scale studies and help inform decisions regarding whether it is worthwhile to commit additional resources to future treatment development. Due to our small sample size, our statistical analytical findings will be interpreted with caution. Sub-study 1c will include sufficient number of subjects to test for treatment efficacy.

Data will be analyzed from all randomized subjects. All statistical tests will be two-tailed. Differences will be considered statistically significant provided a p-value of 0.05 or less is obtained. The significance level for the tests will be adjusted with a Bonferroni correction for multiple comparisons, if needed. Data will be analyzed using SPSS version 27.

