## **17. POTENTIAL BENEFITS**

For the study participant, FoTv and mQFPD may potentially provide direct benefit by reducing the severity of their illness as measured by duration of fever, risk of hospitalization, intubation or death.

Fo-Tv can potentially accelerate, prolong, or enhance the quality of immune responses to vaccine antigens and improve the efficacy of vaccines in individuals with reduced or weakened immune responses as measured by laboratory testing and/or reduce severity of vaccine side effect profile as measured by symptoms scoring.

It is also possible that there may not be any direct benefit for study participants.

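### In sub-study 1c the supporting mixed model focuses on treatment by Time, while the side-effect objective is a difference in level between arms, so it may not confirm a true reduction

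*Combined protocol and SAP*

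**What the plan says.** - **Objective.** Section 6 lists among the primary objectives of 1c "Reduction in side effects from COVID-19 vaccination". Section 17 describes the same benefit as the potential to "reduce severity of vaccine side effect profile as measured by symptoms scoring". Section 9, Statistical Methods And Considerations, names vaccine side effects among the main analysis aims.
- **Timing.** Section 9, Test Product Dose and Route of Administration, has four days of dosing in 1c, "starting with the day of the first vaccination". Section 9, Sub-study 1c, supplies a daily diary with the medication package and names no diary day before the first dose.
- **Possible earlier score.** Section 9, Clinical Assessments, item 4, has COVID-19 symptom scores reported at the screening call. Unlike item 5 (vital signs), item 4 is not restricted to 1a and 1b. Nothing says whether this score is analysed with the diary scores.
- **Analysis.** One text in Statistical Methods And Considerations serves all three sub-studies. It first compares the arms with Wilcoxon-Mann-Whitney tests. It then brings in a mixed model to confirm them, because the rank tests drop participants with missing follow-up. Of that model it says: "The two arms will be compared over time with a focus on the treatment by Time interaction effect". It describes individual intercepts, glossed as baseline values, and individual slopes.

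The plan does not give the coding of Time, the side-effect summary (mean, peak, AUC or incidence) or the window.

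**The concern.** A treatment-by-Time term asks whether the arm difference changes over days. A reduction in side effects is a statement about the size of that difference. The two questions coincide when the series starts with a pre-treatment value at which the arms are equal, as with antibody titre. They separate when every modelled score follows the first dose.

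At stake is how the 1c side-effect result is read. If the rank tests show a true benefit, the model meant to support them may be null because the benefit is steady. If the benefit wanes as reactions resolve, the model may be significant with a sign that reads as slower recovery on FoTv. The plan has no rule for reconciling the two.

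**Working it through.** **Inputs from the documents.** Tests are two-sided at 0.05 ("All statistical tests will be two-tailed"; "Differences will be considered statistically significant provided a p-value of 0.05 or less is obtained"). Allocation is 1:1 ("randomize subjects into one of the two treatment groups with equal probability"). "A total of 266 subjects (133 FoTv and 133 placebo) will be enrolled in sub-study 1c", so n = 133 per arm; with the plan's 20% dropout, 133 × 0.8 = 106.4, so n = 106. Results for 106 follow in brackets. The 266 cannot be reproduced, because the plan gives no numeric effect size, power, correlation or number of time points.

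**Assumptions (not in the documents).** Daily scores are normal with SD 1 and equal correlation ρ = 0.5 (range 0.3 to 0.7). The effects are those stated in each step. Let d be the vector of daily arm differences (FoTv minus placebo) over k days, and S the sum of (t − mean t)² over days.

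**Formulas.**
- Mean score: estimate = mean of d; SE = √[(2/n)(1 + (k − 1)ρ)/k].
- Linear treatment by Time: estimate = Σ(t − mean t)d / S; SE = √[(2/n)(1 − ρ)/S].
- Categorical treatment by Time: joint test of the k − 1 day-to-day changes in d.

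Power for the first two comes from the non-central t distribution, and for the third from the non-central F.

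**1. Constant reduction, post-dose scores only** (d = −0.35 on four days).
- Mean: SE = √[(2/133)(2.5/4)] = 0.0969; ratio −0.35/0.0969 = −3.61; power 95%. For n = 106: SE 0.1086, ratio −3.22, power (89%).
- Linear interaction: Σ(t − 1.5)(−0.35) = 0, so the estimate is 0 and power equals alpha, 5% (5%).
- Categorical interaction: all day-to-day changes in d are 0, so power is 5% (5%).
- For ρ from 0.3 to 0.7 the mean test has 98% to 90% (96% to 82%). The interaction stays at 5%, which is algebra and does not depend on the effect size.

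**2. The same reduction with a pre-dose score added** (d = 0, then −0.35 on four days; the pre-dose score also has SD 1).
- Linear: estimate −0.70/10 = −0.07; SE = √[(2/133)(0.5)/10] = 0.0274; ratio −2.55; power 72% (62%).
- Categorical: 83% (72%).

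The interaction does detect a constant effect here.

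**3. Fading reduction, post-dose scores only** (d = −0.5 × (1, 1, 0.6, 0.3, 0.15, 0.05, 0), days 0 to 6).
- Linear: Σ(t − 3)d = 2.675; S = 28; estimate +0.0955; SE = √[(2/133)(0.5)/28] = 0.0164; ratio +5.83. It is significant in over 99.9% (99.9%) of trials, with FoTv declining more slowly although its scores are never higher.
- Over the first four days only: 0.625/5 = +0.125; SE 0.0388; ratio +3.22; 89% (82%), same direction.

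**4. The fading reduction with a pre-dose score added.**
- Seven diary days, linear: 1.9/42 = +0.0452; SE = √[(2/133)(0.5)/42] = 0.0134; ratio +3.38; 92% (85%), still in the direction of slower decline.
- Four diary days, linear: estimate −0.01, and total rejection is about 7% (6%), close to alpha.

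**5. Mean score under the fading profile, post-dose.**
- Four-day window: −0.3625/0.0969 = −3.74; power 96% (91%).
- Seven-day window: −0.2214/0.0927 = −2.39; power 66% (56%).

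The mean always has the right sign, but a long window dilutes it.

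**The case against.** The strongest reply is that the plan already tests level. The Wilcoxon-Mann-Whitney tests compare the arms directly, and safety data are also compared at each time point. For a 0.5 SD reduction a single-day rank test has roughly 94% to 98% power. This stands. A reader might infer that 1c contains no valid test of a side-effect reduction, or that a true benefit would be missed altogether. The documents do not support that, because the mixed model comes second and is supportive.

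A reader might also infer that every score is post-treatment and that the interaction therefore has no power at all. That goes beyond the text. No first diary day is stated, a symptom score is taken at screening, adverse effects are recorded at baseline in 1c, and the model's intercepts are called baseline values. With a pre-dose score and categorical Time, a constant reduction is detected (step 2). The 5% figure belongs to post-dose-only models.

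The reply does not remove the point. The screening item concerns COVID-19 symptoms, and the plan does not put it in the model. The reference to slopes points to linear Time, under which even a pre-dose score leaves the sign dependent on diary length (step 4).

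A focus on the interaction does not forbid reporting a treatment term, and the interaction does respond to effects that build or wane. But the plan makes no other contrast in this model the one of interest, and the interaction's sign is not a measure of benefit.

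**Conclusion.** The point holds as a mismatch between the supporting model and the objective. For 1c side-effect scores, the contrast that the plan emphasises tests a different hypothesis from the rank tests it should confirm. It can fail to confirm a true reduction or appear to contradict it.

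That post-dose-only models cannot see a constant reduction is exact. The power figures rest on assumed effects, a common correlation and normal scores, whereas the plan itself expects many outcomes to be non-normal. The wrong-sign result depends on a fading profile and on linear Time. With a pre-dose score it appears over seven days but not over four.

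This should be corrected before analysis. It does not invalidate the sub-study.

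**What to change.** Add to Statistical Methods And Considerations, for 1c vaccine side-effect scores:

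- The treatment effect is the arm difference in the mean (or AUC) of daily symptom scores over a fixed window after the vaccination at which study product starts. It is estimated in the mixed model as the treatment effect averaged over day, with day categorical.
- Any pre-vaccination score enters as a covariate, not as a time point.
- Treatment by day is reported descriptively.

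Keep treatment by Time for outcomes with a pre-treatment sample, such as antibody titre, which Section 9 draws at baseline.

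The cost is a sentence or two in the plan and no new data. The drawback is dilution of an effect confined to a day or two: in step 5, power falls from 96% to 66% as the window grows from four to seven days. The window should therefore be short and fixed before unblinding, and the daily estimates would still show a brief effect.

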#### **Sub-study 1c:**

This sub-study will include 266 subjects as well as an additional 53 participants to account for an anticipated 20% rate of study dropout. Number of subjects was adjusted due to recent introduction of the vaccination booster shot and availability of extra funding which allows us to expend study aims to further test of the treatment efficacy.

For other objectives of sub-study 1c, sample size was determined using the RMASS program (<http://tigger.uic.edu/~hedecker/ml.html>)

Based on our sample size estimation, we are confident that the enrollment of 66 (1a/1b) or 266 (1c) participants will provide a sufficient number of subjects to evaluate these outcomes with medium effect size while also ascertaining safety (Tubert-Bitter et al., 2000; Zhang P, 2003).

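### Sub-study 1c pools three vaccine regimens, but its antibody tests carry no regimen term; stratifying by regimen would recover precision at little cost

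*Combined protocol and SAP*

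**What the plan says.** Section 10 admits to 1c any adult scheduled for COVID-19 vaccination, with no restriction on regimen. Under Sample Size Justification the sponsor acknowledges that boosters changed the population: "Number of subjects was adjusted due to recent introduction of the vaccination booster shot".

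Clinical Laboratory Measurements (section 9) sets three draw schedules for 1c:

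| Regimen | Draws |
|---|---|
| Single dose | baseline, day 14, day 28, 6 months |
| Two doses | baseline, day 14, two weeks after dose 2, 6 months |
| Booster | baseline, day 3, day 14, 6 months |

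Statistical Methods And Considerations names the balancing factors: "For sub-study 1c only, equal number of subjects based on age" and BMI. It names antibody titre among the main targets: "The primary aims of our data analytic strategy will be directed toward assessing the safety of the interventions, antibody titers". For the test, "Wilcoxon-Mann-Whitney rank-sum test will be used to analyze treatment arm versus control arm across study visits and sites", and a mixed model "will be used to confirm the results of the nonparametric tests". In that model, "The two arms will be compared over time with a focus on the treatment by Time interaction effect". Regimen does not appear as a stratum, covariate or subgroup, and the coding of Time is not given. Section 6 lists a higher antibody peak and a slower later decline among the primary objectives of 1c.

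**The concern.** Recipients of a first single dose, a two-dose course and a booster may differ widely in titre level and in how far titre rises. If they do, and the analysis ignores regimen, the between-regimen spread is left in the error term of the arm comparison. The rank-sum test on raw titres is exposed to differences in level. A test on change from baseline, or a treatment-by-Time contrast, is exposed to differences in rise.

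There is also a gap in definition. One draw per regimen has no counterpart in the other two, and the plan does not say how it enters a pooled Time effect. At stake is the power of a primary antibody comparison that the sponsor says is adequately sized: "will provide a sufficient number of subjects to evaluate these outcomes with medium effect size".

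**Working it through.** **The plan's own figure.** The 266 (133 per arm) cannot be rebuilt. The text names a program and a medium effect, but gives no power, numeric effect size, SD, correlation or number of visits. With d = 0.5 and two-sided 0.05, a two-sample comparison needs 63, 85 or 104 per arm for 80%, 90% or 95% power.

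**Inputs from the documents.** 133 per arm, 1:1, two-sided 0.05, 20% dropout, three regimens, no regimen term.

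**Assumptions.** Medium effect is d = 0.5. Log titre has within-regimen SD 1 at each visit and baseline-to-day-14 correlation 0.5, so the SD of change is √(1 + 1 − 2 × 0.5) = 1. A share p of subjects are boosters, whose rise differs from that of the other two regimens by g SD.

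**Formula.** Omitting regimen adds V = p(1 − p)g² to the variance of change, so the effective effect size is d/√(1 + V). With complete data the baseline-to-day-14 treatment-by-visit contrast equals the arm difference in mean change, so V applies to it. Power is from the noncentral t.

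**Equal thirds (p = 1/3, so p(1 − p) = 0.222):**

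| g | V | Effective d (d = 0.5) | Power, 133 per arm | Power, 106 per arm |
|---|---|---|---|---|
| 0 | 0 | 0.500 | 98.2% | 95.2% |
| 0.5 | 0.056 | 0.487 | 97.7% | 94.1% |
| 1 | 0.222 | 0.452 | 95.7% | 90.6% |
| 2 | 0.889 | 0.364 | 84.0% | 75.1% |

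The 106 applies if 266 are enrolled and 20% drop out (133 × 0.8 = 106.4).

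**Sensitivity.**
- Smaller effect: d = 0.345, chosen because it gives 80% power at 133 per arm with no gap. Power falls to 71.8% (g = 1) and 53.2% (g = 2).
- 90% boosters: V = 0.09 × g². At d = 0.5 and 133 per arm, power is 97.3% (g = 1) and 93.6% (g = 2).
- One regimen only: V = 0, no loss.

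**Simulation on change from baseline** (2,500 trials, equal thirds, 133 per arm, d = 0.5):

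| Regimen gap | Rank-sum | van Elteren | Contrast, no regimen | Contrast, regimen-by-visit |
|---|---|---|---|---|
| None | 98.0% | 97.8% | 98.5% | 98.4% |
| Constant 2 SD | 97.9% | 97.5% | 98.5% | 98.5% |
| Rise, 1 SD | 95.0% | 97.8% | 96.4% | 98.6% |
| Rise, 2 SD | 81.5% | 97.5% | 84.1% | 97.9% |

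On raw titres (3,000 trials), a constant gap does matter to the rank-sum test: 95.4% unstratified against 97.5% stratified at 1 SD, and 80.4% against 97.7% at 2 SD. Type I error ran from 4.4% to 5.8% over all change-score scenarios.

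**Does restricting to shared visits help?** The variance of a mean of k equally correlated visits is (1 + (k − 1)ρ)/k. Going from three post-baseline draws to the two shared ones at ρ = 0.5 changes it from 0.667 to 0.750, a rise of 12.5%. The rise is 22% at ρ = 0.3 and 2% at ρ = 0.9. Restriction makes Time comparable across regimens but does not gain precision.

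**The case against.** The strongest reply is that the benefit is unknown and may be trivial. The documents give no regimen mix and no titre gap, and equal thirds is only a convenient assumption. At d = 0.5 and 133 per arm, a rise gap of 0.5 to 1 SD costs about 0.5 to 2.5 points. The large losses need a 2 SD gap or a smaller effect than the plan implies. This stands, and it limits how hard the point can be pressed.

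Second, the statistical text is generic to all three sub-studies. The rank-sum sentence refers to sites although 1c has one site. The text does not say whether titres are tested raw or as change, and it does not single out day 14. The contrast worked above is therefore one reasonable reading. This also stands. The plan is silent on regimen; it does not rule regimen out.

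Third, a reader might infer that the pooled analysis should keep only the three shared visits and that doing so would sharpen it. The documents do not support that. Restriction gains no precision, and it would take the day-28 and post-dose-2 draws out of the pooled contrast although peak response is a listed primary objective. Even 6 months is shared only loosely: the two-dose schedule does not say from which dose it is counted.

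**Conclusion.** The point holds as an improvement in efficiency and definition. The stated 1c antibody tests omit a factor that sets each subject's draw schedule and may well drive titre. At d = 0.5, 133 per arm and equal thirds, the cost runs from about half a point of power (0.5 SD rise gap) to about 14 points (2 SD). It is larger for smaller effects, smaller when one regimen dominates, and near zero on change from baseline when the gap does not vary over time. The mix, the gaps and the value of d are all assumed.

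Two stronger readings should be resisted:
- **That pooling biases or invalidates the comparison.** It does not. Allocation is randomized within a mixed population, and simulated type I error stays near 5%.
- **That the plan lines up visits by order, matching a booster's day-3 draw with others' day 14.** If it did, and there were no effect yet at day 3, the second-visit effect with one third boosters would shrink to 0.5 × 2/3 = 0.333 and power to 77%. But the plan never states this coding, and its description of slopes as change over time is equally compatible with time in days.

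**What to change.** For the 1c antibody analysis, specify before unblinding:

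1. Stratify the rank-sum test by scheduled regimen (van Elteren), and state whether it is applied to raw titre or to change from baseline.
2. Add regimen and regimen-by-visit terms to the mixed model, with visits aligned by time since vaccination rather than by visit order.
3. For the peak objective, name one peak visit per regimen: for example day 28 for single-dose, two weeks after dose 2 for two-dose, and day 14 for booster. Use 6 months for decline, stating the dose from which it is counted. Combine the within-regimen treatment contrasts through the stratified analysis.

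This is SAP text only. Regimen must already be known to schedule the draws, so no subjects, visits or assays are added. The cost is a few degrees of freedom, and a very small regimen group may have to be merged under a rule written in advance. When regimen made no difference, stratifying or adding the terms changed simulated power by less than 1 point.
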